4.3. Pharmacodynamic and Pharmacokinetic endpoints

Pharmacodynamic endpoints:

Plasma and serum samples will be collected for summary and exploratory analysis by the Primary Immunodeficiency lab at UZ Gent and the VIB-UGent Inflammation Research Center (IRC) as appropriate (e.g. descriptive statistics, compare change from baseline between the two treatment arms), may include but are not limited to:

- anti-drug antibodies (ADA) – D1 and long-term follow-up serum samples (Summary only to indicate presence or not)
- Local safety labs such as D-dimers, LDH, ferritin, CRP, fibrinogen, eosinophils, lymphocytes
- Cytokines and biomarkers (from selected centres) on D1, and D6 (or at hospital discharge, if earlier) and follow up
 - o Cytokines may include, but not limited to:
 - IL-1 β , IL-1RA, IL-2, IL-8, IL-6, TNF α , GM-CSF, G-CSF, IP-10, MCP-1, MIP-1 α , IFN γ , and IL-10
 - o Biomarkers may include, but are not limited to
 - sRAGE, Angiopoietin-2, KL6, GDF-15, suPAR.
- Immunomonitoring (from selected centers) on D1, and D6 (or at hospital discharge, if earlier) and follow up will include
 - o flow cytometry analysis of numbers of peripheral blood lymphocyte and monocyte subsets, and their activation status by flow cytometry
 - o ELISPOT assays to measure the number of IFN γ , TNF α , IL-2 and GM-CSF producing CD4 and CD8 T cells following restimulation of frozen and thawed peripheral blood mononuclear cells (PBMC) with a SARS-CoV2 megapool of immunogenic peptides.

5. Study design

5.1. Description of study design

This is phase 4 academic, prospective, randomized, open-label, interventional study designed to investigate the efficacy of sargramostim (Leukine®) in improving oxygenation and short- and long-term outcome of COVID-19 patients with acute hypoxic respiratory failure. There are currently no treatments directed at improving lung repair and local immunity in COVID-19 patients, and no treatment that attempt to halt the progression from manageable acute hypoxic respiratory failure to ARDS in patients with COVID-19 infection. **Justification for our objective** is that preventing progression from early acute hypoxic respiratory failure to ARDS could have a huge impact on the foreseeable overflow of the ICU units, that is already happening in some countries and is bound to happen on a global scale.

The **hypothesis of the proposed intervention** is that GM-CSF has profound effects on antiviral immunity, can provide the stimulus to restore immune homeostasis in the lung with acute lung injury post COVID-19, and can promote lung repair mechanisms, that lead to a 25% improvement in lung oxygenation parameters. This hypothesis is based on experiments performed in mice showing that GM-CSF treatment can prevent mortality and prevent ARDS in mice with post-viral acute lung injury.

We will randomize patients with confirmed COVID19 with acute hypoxic respiratory failure (saturation below 93% on minimal 2 l/min O₂ or PaO₂/FiO₂ <350) to receive sargramostim 125mcg twice daily for 5 days as a nebulized inhalation on top of standard of care (active group), or to receive standard of care treatment (control group). Upon progression of disease to requiring non-invasive or invasive mechanical ventilatory support within the 5 day period, in patients in the active group, inhaled sargramostim will be replaced by intravenous sargramostim 125mcg/m² body surface area until the 5 day period is reached.

Dosing of inhaled and systemic sargramostim are based on prior experience of this drug in patients with pulmonary alveolar proteinosis (inhaled) and with pneumonia associated ARDS (inhaled and intravenous). The inhaled route is preferred first, because high local concentrations of GM-CSF have a favourable effect on lung immunity, lung homeostasis and lung repair. The switch to intravenous treatment with deterioration requiring initiation of mechanical ventilation is necessitated by the fact that patients with COVID-19 poorly tolerate ventilation in the absence of high level positive end expiratory pressure (PEEP), especially when they develop ARDS. For giving the sargramostim via inhalator in a ventilated patient, this would involve PEEP-free ventilation for at least 10-15 minutes, which will not be tolerated in COVID-19 associated severe hypoxic respiratory failure and/or ARDS according to expert opinion ([name]. [name], Intensive Care Unit, UZ Ghent).

To measure the effectiveness of sargramostim on restoring lung homeostasis, the **primary endpoint** of this intervention is **measuring oxygenation** after 5 days of inhaled (and intravenous) treatment through assessment of pretreatment and post-treatment ratio of PaO₂/FiO₂ and through measurement of the P(A-a)O₂ gradient, which can easily be performed in the setting of clinical observation of patients admitted to the COVID -19 ward or ICU COVID-19 unit. Supplemental oxygen use will be recorded, and if needed A-a gradient will be normalized against expected age- and supplemental oxygen dependent A-a gradient. During the 5 day treatment period, we will perform daily measurements of oxygen saturation (pulse oximetry) in relation to FiO₂, and the slope of alterations in this parameters could also be an indicator that our hypothesis is correct. If the patient leaves hospital prior to the day 6 analysis point, oxygenation at day of discharge will be used as value for measuring primary endpoint.

Comparison will be between active group A receiving sargramostim on top of standard of care and control group B receiving standard of care.

Data from the Wuhan COVID-19 epidemic show that patients that deteriorate are facing a prolonged period of mechanical ventilation. Therefore, from day 6 onwards, progressive patients in the active group will have the option to receive an additional 5 days of IV sargramostim, based on the treating physician's assessment. This group will be called group C. In the control group with progressive disease requiring non-invasive or invasive mechanical ventilatory support or developing ARDS, from day 6 onwards, the treating physician will have the option to initiate IV sargramostim 125mcg/m² body surface area once daily for 5 days. This group will be called group D. Comparisons of Group A (early 5 day intervention with sargramostim) with Group D (late 5 day intervention with sargramostim) will also be very informative.

5.2. End of Study Definition

5.2.1. For an individual subject

The subject has completed the study if he or she has completed all phases of the study, including the last visit (week 10-20 clinical follow up visit) or the last scheduled procedures, as described in this protocol (see section "9. Study Specific Procedures").

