3.2. Secondary Objectives

- to study if early intervention with sargramostim is safe (number of AEs/SAEs)
- to study if early intervention with inhaled sargramostim affects clinical outcome defined by
 Duration of hospital stay
 Mean and median change in 6-point ordinal scale between day 1 and day 6
 Mean and median change in clinical sign score between day 1 and day 6
 Time to clinical sign score <6 maintained for 24h
 Mean and median change of SOFA score between day 1 and day 6 or between day 1 and day 10.
 Mean and median change NEWS2 score between day 1 and day 6 or between day 1 and day 10.
 Time to NEWS2 score less than 2 for at least 24h
- to study if early intervention with sargramostim affects the rate of nosocomial infection
- to study if early intervention with inhaled sargramostim affects progression to mechanical ventilation and/or ARDS
- to study if treatment with sargramostim affects all cause mortality rate at 28 days and 20 weeks post inclusion
- to study if treatment with sargramostim affects features of secondary haemophagocytic lymphohistiocytosis, as defined by Hs score (temp, organomegaly, cytopenia, triglycerides, fibrinogen, ferritin, AST and known immunosuppression)
- to study if treatment with sargramostim has a favourable effect on long term 10-20 week follow up

4. End Points + Time Points

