-to study if treatment with sargramostim affects all-cause mortality rate at 4 and 20 weeks post inclusion.

-to study if treatment with sargramostim affects features of secondary haemophagocytic lymphohistiocytosis.

A large subset of patients with severe COVID-19 developing respiratory failure might have a cytokine storm syndrome, designated as secondary haemophagocytic lymphohistiocytosis (sHLH). sHLH is an under-recognised, hyperinflammatory syndrome characterised by a fulminant and fatal hypercytokinemia with multi-organ failure. Cardinal features of sHLH include unremitting fever,

cytopenias, and hyperferritinaemia; hypertriglyceridemia, pulmonary involvement can present as ARDS. A cytokine profile resembling sHLH is associated with COVID-19 disease severity, characterised by increased interleukin (IL)-2, IL-7, granulocyte-colony stimulating factor, interferon- γ inducible protein 10, monocyte chemoattractant protein 1, macrophage inflammatory protein 1- α , and tumour necrosis factor- α .

Predictors of fatality from a recent retrospective, multicentre study of 150 confirmed COVID-19 cases in Wuhan, China, included elevated ferritin (mean 1297.6 ng/ml in non-survivors vs 614.0 ng/ml in survivors; $p < 0.001$) and IL-6 ($p < 0.0001$), suggesting that mortality might be due to virally driven hyperinflammation.

To address the effect of sargramostim treatment on sHLH, we will measure levels of ferritin, these chemokines and cytokines at the beginning of the trial day 0 and after the initial 5 day treatment. PBO including leukocytes and lymphocytes are performed on a routine clinical basis in these patients.

- to study if treatment with sargramostim has a favourable effect on long term 10-20 week follow up

At 10-20 weeks after Day 1, patients will be seen on routine check-up by pulmonologist, who will perform a clinical exam, pulmonary function tests (including FVC, TLC and diffusion capacity), a laboratory (ferritin, lymphocytes, leukocytes) and a 6 minutes walk test and HRCT if done per standard of care.

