9.3. Overview of collected data

1. patient demographics
 - age, sex, ethnicity, day of admission
2. day of COVID-19 PCR positivity, and conversion to negative
2. patient biometry
 - weight, length, BMI, body surface area
3. Clinical and laboratory parameters on screening day and during trial
 - first day of illness, potential source of infection
 - clinical examination findings (cyanosis, crepitation's and rales, heart murmurs, peripheral edema)
 - vital signs (temperature, blood pressure, heart rate, breathing rate)
 - pulse oximetry data (SaO₂)
 - clinical blood gas sampling (PaO₂, PaCO₂, HCO₃)
 - clinical chemistry sampling (ferritin, leukocyte formula, platelets, kidney and liver function, fibrinogen, triglycerides)
 - Chest X-ray and/or CT characteristics and radiology clinical report
 - in case of admission to ICU : invasive monitoring data (arterial blood pressure, PCWP, continuous O₂ saturation, continuous ECG, ventilatory parameters (tidal volume, FiO₂, PEEP pressure, peak pressure, minute ventilation)
4. All standard care drugs used during the trial and on day of enrolment of the trial, including oxygen flow rate.
5. Basic clinical data on prior medical history (prior lung diseases, smoking history, prior lung function measurements (preferentially within 5 preceding years), prior gas exchange measurements) and medication use will be collected from electronic medical record.
6. Study specific measurements

On serum samples from selected centers, at each of the indicated timepoints exploratory analysis may include but is not limited to:

- Anti-drug antibodies (ADA) (D1-D6-FU) using ELISA
- Quantification of sRAGE (D1-D6-FU) using ELISA
- Quantification of Ang2 (D1-D6-FU) using ELISA
- Quantification of MUC1 (D1-D6- FU) using ELISA
- Quantification of GDF15 (D1-D6- FU) using ELISA
- Quantification of suPAR (D1-D6-FU) using ELISA
- Quantification of cytokines GM-CSF, IL-1b, IL1RA, IL-6, IL-8, IL-10, IL12p40, IL17A, IL-18, IL23p19, CCL2, CXCL9, CXCL10, INFgamma, TNF (D1-D6-FU) using Luminex at VIB-UGhent.
- Quantification of IFNalpha2 (D1-D6-FU) using SIMOA
- Quantification of GM-CSF (D1-D6-FU) using MSD.
- Quantification of S1 specific IgG and IgA antibodies (D1-D6-FU) using ELISA
- Quantification of NCP specific IgG (D1-D6-FU) using ELISA
- will be measured on samples collected at the various centers at day 1 or day 6 or discharge (whichever comes first) and at 12-22 weeks follow up visit.

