At least 25% reduction from baseline, at least 33% reduction from baseline, and at least 50% reduction from baseline in P(A-a)O_2 gradient and pathological gradient on Day 6 will be summarized for mITT population.

Survival status will be collected up to follow-up period (20 weeks after day 1). Death is considered as an event. All the mortality events and cause of death will be listed by treatment group and by patient. Number of patients died and survival time will be summarized by treatment group. Survival time will also be listed by patient. Risk and risk difference of all causes mortality by Day 28 and during the study period will also be summarized.

The hazard ratio will be estimated by the Cox proportional hazards model with treatment group as a covariate in the model. Relevant hazard rates, hazard ratio between treatment groups and associated p-values will be tabulated.

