14.2. Reporting requirements

14.2.1. AE reporting

AE's will be recorded from the first drug administration until the end of the study, as defined in section 5.2.

Special attention will be given to those subjects who have discontinued the study for an AE, or who experienced a severe or a serious AE. All AE's should be recorded in the patient's file and in the CRF.

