14.2.2. SAE reporting

SAE's occurring during the entire study period will be reported as below.

All serious adverse events (initial and follow up information) and pregnancies occurring during this study must be reported by the local Principal Investigator within 24 hours after becoming aware of the SAE to:

- The local ethics committee (it is the responsibility of the local PI to report the local SAE's to the local EC)
- HIRUZ CTU of the University Hospital Ghent
- The National Coordinating Investigator (in case of multicenter studies)
The company Partner Therapeutics that provides the IMP

This reporting is done by using the appropriate SAE form. For the contact details, see below.

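### The last scheduled contact may fall as early as week 10, so deaths belonging to the 20-week mortality endpoint can be missed, and the study-period risk and AE counts may cover unequal windows

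*Protocol*

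**What the plan says.** Section 3.2 sets the objective: "to study if treatment with sargramostim affects all cause mortality rate at 28 days and 20 weeks post inclusion". Section 4.2 repeats it as an endpoint: "to study if treatment with sargramostim affects all-cause mortality rate at 4 and 20 weeks post inclusion". Four weeks is 28 days, so the two agree.

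Section 12.2 says survival status is gathered up to 20 weeks after day 1. It plans survival times, a Cox model with treatment as covariate, and this summary: "Risk and risk difference of all causes mortality by Day 28 and during the study period will also be summarized". It names no risk at 20 weeks.

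Section 5.2.1 says a subject has completed the study after all its phases, "including the last visit (week 10-20 clinical follow up visit) or the last scheduled procedures". The schedule in 9.4 has one follow-up column, 10 to 20 weeks after D1, and nothing after it. The tracing steps in 7.1.2 apply when a patient fails to attend that visit.

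On safety, section 14.2.1 states: "AE's will be recorded from the first drug administration until the end of the study, as defined in section 5.2". Section 14.2.2 states: "SAE's occurring during the entire study period will be reported as below". The safety endpoint in 3.2 and 4.2 is the number of AEs and SAEs, compared between groups A and B.

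The window is not the same everywhere. Sections 5.2.1, 7.1.2, 9.2, 9.4 and 11 give weeks 10 to 20. Section 1.7 gives 10 to 22 weeks to the final visit, and section 9.3 refers to samples taken "at 12-22 weeks follow up visit".

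**The concern.** The statistics section relies on 20-week survival status that the visit schedule does not obtain for everyone. A patient who attends at week 10 has completed the study and, having attended, does not trigger the tracing steps. If that patient dies at week 14, no described procedure brings the death into the data.

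Two summaries are affected. The mortality risk over the study period is a crude proportion taken over whatever period each patient was followed, and clinic scheduling sets that period. The AE and SAE counts may have the same weakness, depending on which end of study 14.2.1 means.

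The end of study, the visit schedule and the AE recording period are protocol matters. An analysis plan can choose how to handle unequal follow-up, but it cannot supply vital status that was not collected.

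**Working it through.** The protocol gives no figure for this point, so there is none to reproduce. The check sets the sections side by side and then measures the windows.

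**1. Survival status (12.2 against 5.2.1 and 9.4).** Collection is promised to week 20. The last scheduled contact is at week v, with v anywhere from 10 to 20. If nothing is collected after the visit, the unobserved share of the 20 weeks is (20 − v)/20:

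| Visit week v | Unobserved share |
|---|---|
| 10 | 10/20 = 50% |
| 12 | 8/20 = 40% |
| 15 | 5/20 = 25% |
| 20 | 0/20 = 0% |

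If visits were spread evenly over weeks 10 to 20 (assumed), the mean visit would be at week 15 and about 25% of the 20 weeks would be unobserved.

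**2. How many deaths this could involve.** The protocol does not give the inputs, so these are assumptions: 20-week mortality of 5% to 20%; 2% to 20% of those deaths after week 10; visits and late deaths independent and spread evenly over weeks 10 to 20, so that half of the late deaths follow the visit.

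- Low end: 80 × 0.05 × 0.02 × 0.5 = 0.04 deaths
- High end: 80 × 0.20 × 0.20 × 0.5 = 1.6 deaths

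In an arm of 40, one missed death moves the risk by 1/40 = 2.5 percentage points.

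**3. Which mortality analyses are exposed.**

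- Day 28 risk: every permitted visit comes after day 28, so status is known for everyone who attends.
- Cox model: unequal follow-up can be handled by censoring at last contact, provided visit timing is unrelated to prognosis.
- Risk over the study period: exposed, because a crude proportion makes no allowance for length of follow-up.
- Risk at 20 weeks: named as an objective and endpoint, but not among the risk summaries in 12.2.

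**4. AE window (14.2.1 against 5.2).** Section 14.2.1 points to section 5.2 as a whole, which has two parts.

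- Under 5.2.1 (the individual subject), windows counted from day 1 run from 10 to 20 weeks: 20/10 = 2.0. With the 22 weeks of section 1.7 the ratio is 22/10 = 2.2. If a visit due at week 20 is missed and rebooked within the 4 weeks that 7.1.2 allows, it is 24/10 = 2.4.
- Under 5.2.2 (last visit of the last subject), early enrolees have longer windows than late ones, with no scheduled contact to fill them.

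Either reading gives unequal windows between patients. Neither implies unequal windows between arms.

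**The case against.** The strongest reply is that 12.2 does provide for survival status to 20 weeks. That stands. A reader might infer that 20-week mortality cannot be obtained, or that late deaths will certainly be lost, and the protocol does not support this. A site could follow 12.2 and look up each patient at week 20. What is missing is any procedure in 5.2.1 or 9.4 that tells it to, so deaths can be missed but need not be.

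A reader might also think the 28-day comparison is at risk because nothing is scheduled between day 10 and week 10. It is not, for patients who attend. For those who do not, 7.1.2 already requires rebooking, telephone calls and, if needed, a letter; what loss remains is common to any design.

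On AEs, one might infer that recording stops for each patient at the visit and that one arm's count is inflated. The first is only one reading of 14.2.1: the phrase "until the end of the study, as defined in section 5.2" does not choose between 5.2.1 and 5.2.2. SAE reporting covers the whole study period and is triggered by awareness of the event, not by a visit. The second has no basis in the protocol. Patients are randomised 1:1 and both arms share one window, so no difference in visit timing is expected, though an open-label trial cannot rule it out. Events in acutely ill inpatients would also be expected to cluster early, which reduces the effect of late differences in follow-up.

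Finally, exposure-adjusted AE rates or a common cut-off may be in the analysis plan, which is not at hand. That could settle the AE analysis. It would not settle the recording period or the missing week-20 contact.

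**Conclusion.** The point holds as an inconsistency within the protocol. The mortality endpoint and 12.2 call for 20-week status, while 5.2.1 and 9.4 let follow-up end at a visit from week 10 with nothing scheduled afterwards. Deaths after an early visit can be missed, and the crude study-period risk covers unequal windows. The end of AE recording is ambiguous; on the 5.2.1 reading, individual windows differ up to twofold.

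The likely size is modest. The estimate of 0.04 to 1.6 deaths among 80 patients rests wholly on the assumed mortality, late share and visit spread, and on nothing being collected after the visit. The primary endpoint, the sample size and, for patients who attend, the 28-day mortality comparison are unaffected. No bias between arms is shown. This is a cheap improvement to secondary endpoints.

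**What to change.** - **5.2.1 and 9.4:** add a vital-status check at week 20 for all randomised patients, whenever the clinic visit takes place, from the hospital record or by telephone using the contact steps in 7.1.2.
- **12.2:** replace the mortality risk over the study period with the risk and risk difference at 20 weeks, to match 3.2 and 4.2. Keep the Day 28 risk and the Cox model.
- **14.2.1:** state whether 5.2.1 or 5.2.2 ends AE recording. Compare AE and SAE counts up to one common study day in both arms (for example week 10, the earliest point at which a patient can complete), or as exposure-adjusted rates, and list later SAEs separately.
- **1.7 and 9.3:** bring 10-22 and 12-22 weeks into line with the 10-20 weeks used elsewhere.

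With a fixed week-20 status for everyone, the mortality window ratio becomes 20/20 = 1.0. The cost is amendment wording and one record check or short call per patient seen before week 20. No clinic visit is added, and sample size and power do not change.

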5.2.2. For the whole study

Overall, the end of the study is reached when the last study procedure for the last subject has occurred: last subject, last visit (LSLV).

As soon as the whole study has ended (cfr. the definition above), the co-ordinating Investigator shall notify the HIRUZ Clinical Trial Unit, so that the Competent Authority and the Ethics Committee can be informed in a timely manner according to the regulatory requirements (within 90 days after end of the study, or if the study had to be terminated early, this period must be reduced to 15 days and the reasons should clearly explained).

5.3. Estimated duration of the study

There is a large number of COVID-19 infected patients that are currently being hospitalized across the globe. In just 9 days time, our COVID-19 ward at Ghent University Hospital has admitted 25 confirmed cases, of which a significant portion (50%) already fulfill eligibility criteria for the current proposed protocol. We therefore believe that given the current ascending part of the epidemiology curve, with numbers of patients rising sharply, there will be no shortage of patients that are eligible. We estimate the study to terminate in 30 weeks, including last clinical follow up visits.

6. Inclusion and Exclusion Criteria

